4.2.2.3 Tipping Point Analysis

Tipping point analyses will also be implemented as a supportive analysis for the primary efficacy endpoint.

The objective of the tipping point analyses is to evaluate the sensitivity of results to departures from the missing at random assumption and to identify the point at which departures cause results to "tip" from statistically significant to statistically non-significant. As such, these tipping

point analyses will only be performed if the primary efficacy analysis results in a statistically significant treatment effect.

For tipping point analyses, data for participants after the intercurrent event date (See Section 3.9) will be changed to missing prior to imputation but will not be changed to non-response after imputation.

The worst-case scenario will be evaluated first. All missing primary endpoint values for study participants randomized to bimekizumab (where missing values include observations after the intercurrent event date and any other missing values) will be imputed as non-responders, while all missing values for placebo-randomized study participants will be imputed as responders. While there is little justification for such an approach, it makes the most putative assumption possible against a bimekizumab treatment effect. After applying this imputation approach, a logistic regression model consistent with the one described for the primary analysis will be applied. If the p-value for the odds ratio of bimekizumab versus placebo remains significant, then no further tipping point analyses are needed.

If this analysis based on the worst-case scenario results in a p-value that is not significant (eg, greater than 0.025), then additional tipping point analyses will be performed to identify the point at which results switch or “tip” from significant to non-significant. Note that each bimekizumab dose of [REDACTED] and [REDACTED] will be compared to placebo independently for these analyses. If one dose regimen is tested at the 0.05 significance level as determined in Section 4.5, then the p-value in this analysis method will be 0.05 instead of 0.025 throughout for that dose. In the tipping point analysis, a shift parameter or delta adjustment is applied to missing, and subsequently imported primary endpoint values (where missing values include observations after the intercurrent event and any other missing values). These delta implemented on the primary endpoint as follows:

1. Data after intercurrent event date (See Section 3.9) will be set to missing.
2. The same MCMC method described in Section 4.2.2.1 (Step 1a) will be implemented for non-monotone (intermittent) missing pattern values, using the same imputation model. This will be based on 100 sets of imputations.
3. Based on the 100 datasets obtained in Step 2, a monotone regression model will be applied (using the same imputation model as in Step 2) as described in Section 4.2.2.1 (Step 1b). This will be based on 1 imputation.
4. Delta adjustments will be made to imputed lesion count values at Week 16, independently in each treatment group as described below.
5. Delta adjusted imputed values will be truncated so that they are within the range of allowable values for each component.
6. Following the delta adjustments for the lesion counts, HiSCR₅₀ will then be derived based on the delta-adjusted multiply imputed data sets obtained for each component.
7. Each of the 100 imputed datasets will then be analyzed using a logistic regression model with factors of treatment group, Baseline Hurley Stage, and Baseline antibiotic use.

8. The results obtained from the 100 logistic regression analyses in Step 7 will be combined for overall inference using Rubin's rules, and the results obtained for each shift parameter will be presented in a single table.
9. Steps 4 to 8 will be repeated so that, at each iteration, missing values are adjusted with a larger delta than at the previous iteration. The process will go on until the p-value for the odds ratio between bimekizumab and placebo is no longer statistically significant (eg, ≥ 0.025). The odds ratio, 97.5% CI (or 95% depending on the significance level being used for testing), and p-values obtained for each value of delta will be combined in one single table.

The delta adjustments result in study participants randomized to bimekizumab with missing data having a lower probability of response compared to study participants randomized to placebo with missing data. Since HiSCR₅₀ response is an endpoint for which high lesion counts are associated with a less favorable outcome:

- A positive adjustment is applied to the imputed value for study participants randomized to bimekizumab in order to increase the imputed value and decrease the likelihood of response.
- A negative adjustment is applied to the imputed value for study participants randomized to placebo in order to decrease the imputed value and increase the likelihood of response.

To start, imputed values within each lesion type, will be adjusted by the same value in each treatment arm. This adjustment will be 5% of the observed range within that lesion type. Depending on the results obtained, this adjustment will be multiplied for step 9 above (2 times, 3 times the initial adjustment) until the p-value is no longer statistically significant.

Additionally, study participants randomized to bimekizumab with an intercurrent event should be set to non-response, after applying the delta adjustment outlined in Step 6 above. This ensures study participants randomized to bimekizumab do not have a higher probability of response in the tipping point analyses compared to the primary analysis (ie, a study participant randomized to bimekizumab who is non-responder in the primary analysis cannot become a responder in the tipping point analyses).

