8.2.3.3 Tipping point analysis

Tipping point analyses will be performed to evaluate missingness assumptions. Various delta adjustments will be made to the assumed responses on the monotone missing data in each treatment group independently with various degrees of plausibility. It will include scenarios where study participants who have missing data and are randomized to bimekizumab have a

lower probability of response compared to study participants who have missing data and were randomized to placebo. This includes the worst-case scenario where study participants who have missing data and are randomized to bimekizumab are considered nonresponders, while study participants who have missing data and were randomized to placebo are considered responders. The goal of the tipping point analysis is to systematically vary assumptions until there is no evidence of a treatment effect (if possible). The plausibility of such required delta adjustment will then be assessed.

Refer to Section 4.2.2 for more details on the methodology.

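### The tipping-point steps move both arms together by one delta, although the plan promises independent adjustment per arm, so a tip cannot be attributed to either arm

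*SAP*

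**What the plan says.** Section 4.2.2.3 sets out the tipping-point analysis of HiSCR50 at Week 16. It runs only if the primary result is significant. A worst case comes first: all missing bimekizumab values fail and all missing placebo values respond. The delta steps follow only if that worst case loses significance.

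On how the deltas vary between arms, Step 4 says: "Delta adjustments will be made to imputed lesion count values at Week 16, independently in each treatment group as described below". Section 8.2.3.3 says the adjustments are "made to the assumed responses on the monotone missing data in each treatment group independently with various degrees of plausibility", and Table 8-1 says the same in its tipping-point row. Section 8.2.3.3 adds that the plausibility of the delta needed to tip the result will be assessed.

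The rule that a programmer would follow comes after Step 9:

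- Direction on active treatment: "A positive adjustment is applied to the imputed value for study participants randomized to bimekizumab".
- Direction on placebo: "A negative adjustment is applied to the imputed value for study participants randomized to placebo".
- Size: "To start, imputed values within each lesion type, will be adjusted by the same value in each treatment arm", with "This adjustment will be 5% of the observed range within that lesion type".
- Escalation: "this adjustment will be multiplied for step 9 above (2 times, 3 times the initial adjustment) until the p-value is no longer statistically significant".

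Step 9 asks for one table with one set of results per value of delta.

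**The concern.** Three places announce arm-by-arm variation, but the instructions have a single free quantity, the multiplier. Whenever bimekizumab leavers are made worse by k steps, placebo leavers are made better by k steps. No step sets the placebo shift to zero, and none moves one arm while the other stays put.

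This matters because the purpose of the analysis is a plausibility judgement. The departure that most readers will want to see is bimekizumab participants with missing data doing worse than MAR predicts, with placebo left at MAR. Unexplained improvement among placebo leavers is much harder to defend, and the plan itself concedes that its worst case, which rests on the same idea, is hard to justify. If the joint path tips, the output cannot show whether the bimekizumab shift alone would have been enough. A result that no bimekizumab-side assumption could overturn may then be reported as tipping.

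**Working it through.** **Reading the rule.** Let k be the multiplier and d be 5% of the observed range for a lesion type. The shift is +k·d on bimekizumab and −k·d on placebo, for k = 1, 2, 3, and so on. The scenarios lie on one diagonal line that heads toward the worst case. The line (k_B, k_P) = (k, 0) is not on it.

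**Reproducing the plan's base figure.** Table 2-1 gives power 0.90 for HiSCR50 at 0.50 v 0.25, N = 140 v 70, two-sided alpha 0.025. With pooled rate (70 + 17.5)/210 = 0.4167, the null SE is √(0.4167 × 0.5833 × (1/140 + 1/70)) = 0.0722. The alternative SE is √(0.25/140 + 0.1875/70) = 0.0668. Then (0.25 − 2.241 × 0.0722)/0.0668 = 1.32, which gives power 0.907. The figure reproduces, and the point does not dispute it.

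**Illustration: inputs.** Rates and sample sizes come from Table 2-1. The following are assumptions that the SAP does not state: the same missing share m in both arms, no intercurrent events, missing participants responding at the arm's rate under MAR, and an unadjusted Wald test on expected counts. The response scale stands in for the lesion-count delta.

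Formula: log OR = ln[r_B/(N_B − r_B)] − ln[r_P/(N_P − r_P)]. SE = √[1/r_B + 1/(N_B − r_B) + 1/r_P + 1/(N_P − r_P)]. The p-value is two-sided normal.

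**At m = 10%** (14 and 7 missing; observed responders 0.50 × 126 = 63 and 0.25 × 63 = 15.75):

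| Scenario | Responders | log OR | SE | p |
|---|---|---|---|---|
| Both at MAR | 70/140 v 17.5/70 | 1.099 | 0.324 | 0.0007 |
| All bimekizumab missing fail, placebo at MAR | 63/140 v 17.5/70 | 0.898 | 0.324 | 0.006 |
| Bimekizumab at MAR, all placebo missing respond | 70/140 v 22.75/70 | 0.731 | 0.306 | 0.017 |
| End of joint path | 63/140 v 22.75/70 | 0.530 | 0.307 | 0.084 |

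The joint path first tips about 70% of the way to the extreme. Bimekizumab responders are then 63 + 7 × 0.30 = 65.1, and placebo responders are 15.75 + 7 × (0.25 + 0.75 × 0.70) = 21.2, with p = 0.025. The same bimekizumab shift with placebo at MAR gives p = 0.003.

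**Other missing shares, 140 v 70:**

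| Missing | All bimekizumab missing fail, placebo at MAR | End of joint path | Reading at 0.025 |
|---|---|---|---|
| 5% | 0.002 | 0.010 | Worst case holds; no delta step runs |
| 8% | 0.004 | 0.038 | Joint path tips; bimekizumab-only cannot |
| 10% | 0.006 | 0.084 | Same |
| 12% | 0.008 | 0.17 | Same |
| 15% | 0.014 | 0.38 | Same |
| 20% | 0.033 | 1.0 | Both tip, bimekizumab-only near its extreme |

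**280 v 70 (0.60 v 0.25), worst case:** p = 0.0016 at 10% missing and 0.0055 at 12%. At 15% (142.8/280 v 25.375/70; log OR 0.604, SE 0.276), p = 0.028. Delta steps would start only at about 15% missing.

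**The case against.** A reader might infer that the plan never examines bimekizumab leavers doing worse with placebo left alone. That is true of the delta steps but not of the plan. The reference-based analysis (Sections 4.2.2.2 and 8.2.3.2) imputes both arms from the placebo model, so placebo follows its own arm while bimekizumab leavers lose their advantage. Nonresponse imputation (Section 8.2.3.1) fails all missing bimekizumab participants without improving placebo. On the 10% illustration, nonresponse imputation gives 63/140 v 15.75/70, p = 0.002. Giving bimekizumab leavers the placebo rate gives 66.5/140 v 17.5/70, also p = 0.002. Both would reassure a reader who sees a joint tip. Each is a single fixed scenario, however, and neither searches for the delta at which the result changes.

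A reader might also infer that plausibility cannot be judged at all, or that a tip is produced wholly by the placebo half. Neither follows. Results are tabulated by delta, so the joint shift can be discussed, and at 10% missing neither half tips on its own (0.006 and 0.017). What is lost is attribution.

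On the wording, independently could mean applied separately within each arm with its own sign, and the text leaves some room by calling the common value a start. But multiplying that same value is the only escalation described. If separate variation was intended, it is not specified.

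Two further points stand. The bias runs against the sponsor, because improving placebo as well is harsher than a bimekizumab-only shift of the same size. And if this arm is tested at 0.05, as Section 4.2.2.3 allows, the 8% example disappears (0.038), while at 20% the bimekizumab-only extreme (0.033) would no longer tip.

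**Conclusion.** The point holds as a mismatch between the promised independent adjustment and a rule with one common delta and one multiplier. Within the delta steps placebo is never at MAR, and a reported tip cannot be assigned to the bimekizumab or the placebo departure.

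Its reach is limited. The analysis is supportive, changes no confirmatory decision and can only overstate fragility; no false efficacy claim follows. Under the stated assumptions it matters for the 140 v 70 comparison from about 8% to 15% missing at alpha 0.025. It does not arise at 5%, and at 20% a bimekizumab-only shift also tips. The 280 v 70 comparison is unaffected up to 12% missing. The missing shares are assumptions, and the illustration leaves out intercurrent events, which the plan treats differently by arm in this analysis, so the thresholds are indicative only.

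**What to change.** In Section 4.2.2.3, replace the common multiplier in Step 9 and in the paragraph on the 5% adjustment by two separate multipliers: k_B = 0, 1, 2, ... for the bimekizumab shift and k_P = 0, 1, 2, ... for the placebo shift, explicitly including the row k_P = 0. Report the p-value in each cell, mark the boundary between significant and non-significant cells, and base the plausibility assessment in Section 8.2.3.3 on that boundary. Step 4, Table 8-1 and Section 8.2.3.3 can then stand as written.

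The cost is SAP wording, more runs of the same program and a grid instead of a single column for each dose comparison. No new data are needed and the primary analysis is untouched. Deleting the claim of independence and justifying the single path would remove the contradiction more cheaply, but the attribution problem would remain.

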4.2.3 Rationale for estimand

Intercurrent events have been identified within the estimands for this study because of their potential to impact efficacy assessments linked with the primary and secondary study objectives. In order to account for the effect of any observed post-randomization intercurrent events on the efficacy analyses, the following estimand strategies will be implemented when evaluating the primary and secondary efficacy endpoints:

- A composite estimand strategy will be used for the primary analysis of the primary and binary secondary endpoints (HiSCR₅₀, HiSCR₇₅, flare, HS worst skin pain response);
- A hypothetical estimand will be used for the primary analysis of the continuous secondary endpoints (CFB in DLQI total score and in "worst skin pain" item for the HSSDD).

4.2.3.1 Composite estimand

A composite estimand strategy as defined in Section 8.2.2 allows incorporation of the two intercurrent events (eg, receipt of systemic antibiotic rescue medication or discontinuation of study treatment due to an AE or lack of efficacy) within the definition of the endpoint. These

intercurrent events are considered meaningful to the efficacy outcome following receipt of study medication. For example, within the proposed composite estimand framework, a randomized study participant who discontinues from study treatment due to lack of efficacy prior to Week 16 will be considered a treatment failure at Week 16 regardless of the lesion count assessment performed at that visit.

The assumptions and robustness of the primary analysis (modified composite estimand as defined in Section 8.2.2) will be assessed through the sensitivity analyses defined in Section 8.2.3. The impact of intercurrent event handling and data imputation methods on endpoint derivation will also be assessed via the analyses of lesion counts and derived HiSCR variables as specified in Section 8.4.2.1 and Section 8.4.1.1, respectively.

4.2.3.2 Hypothetical estimand

The hypothetical estimand is defined in Section 8.3 and involves a data-driven approach to account for the potential impact of intercurrent events (eg, receipt of systemic antibiotic rescue medication or discontinuation of study treatment due to an AE or lack of efficacy) on the analysis of continuous efficacy endpoints. Under this framework, outcomes for study participants without an intercurrent event are analyzed as observed. Conversely, outcomes for study participants with an intercurrent event are imputed via a multiple imputation model, ie any recorded data on or after the intercurrent event will be set to missing and imputed via multiple imputation following the strategy established in Section 4.2.2.1.

4.2.4 Dates and times

For analyses of AEs and concomitant medication usage, a complete date is required in order to correctly identify the AE or medication as occurring during treatment or not, and for correctly assigning an AE or concomitant medication to the Initial Treatment Period or Maintenance Treatment Period.

For purposes of imputing missing components of partially-reported start and stop dates for AEs and for medication use, the algorithms listed below will be followed. Start and stop dates of AEs or concomitant medication will be displayed as reported in the participant data listings (ie, no imputed values will be displayed in data listings).

Partial AE and concomitant medication start dates will be imputed as follows:

- Imputation of Partial Start Dates
 - If only the month and year are specified:
 - If the month and year of first dose of study medication is the same as the month and year of the partial start date, then use the date of first dose of study medication,
 - Else, if the month and year of the partial start date are the same as the month and year of a study medication switch date, then use the date of study medication switch,
 - Otherwise, use the 1st of the month of the partial start date;
 - If only the year is specified:
 - If the year of first dose of study medication is the same as the year of the partial start date, then use the date of first dose of study medication,

-
- Else, if the year of the partial date is the same as the year of a study medication switch date, then use the date of study medication switch,
 - Otherwise, use the 1st of January of the year of the partial start date;
 - If the start date is completely unknown:
 - If the stop date is unknown or not prior to the date of first dose of study medication, then use the date of first dose of study medication,
 - If the stop date is prior to the date of first dose of study medication, then use the 1st of January of the year of the stop date.
 - Imputation of Partial Stop Dates
 - If only the month and year are specified, :
 - Use the last day of the month of the partial stop date;
 - If only the year is specified
 - use December 31st of the year of the partial stop date;
 - If the stop date is completely unknown,
 - Do not impute the stop date.

Note that if the stop date or the imputed stop date is prior to the imputed start date, then follow the procedure outlined below:

- If only the year of the start date is specified:
 - If the year of start date is the same as the year of first dose of study medication and the imputed stop date is after the date of first dose of study medication, then set the start date to the date of first dose of study medication,
 - Otherwise, set the 1st January of the year of the start date;
- If only the month and year of start date are specified:
 - If the month and year of the start date is the same as the month and year of first dose of study medication and the imputed stop date is on or after the date of first dose of study medication then set the start date to the date of first dose of study medication,
 - If the month and year of the start date is the same as the month and year of first dose of study medication and the imputed stop date is before the date of first dose of study medication then set the start date to the 1st of the month of partial start date.

Missing start times for medications will be imputed as 00:00h or with the time of dosing for events occurring on the date of IMP administration in case of missing hour and minute. Otherwise start times with only missing minutes will be imputed with :00 or with the minutes of dosing for events occurring on the date and hour of IMP administration.

In the event of ambiguity or incomplete data that makes it impossible to determine whether a medication was concomitant or an AE was treatment emergent, the medication will be considered as concomitant or the AE will be considered treatment emergent. Similarly, in the event of ambiguity or incomplete data which makes it impossible to determine whether a

medication or AE is to be assigned to the Initial Treatment Period or to the Maintenance Treatment Period (or both, for medications), then the medication will be assigned to both Treatment Periods, and the AE will be assigned to the Initial Treatment Period.

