3.9 Definition of an intercurrent event

Handling of intercurrent events is one of the key elements for the analysis of efficacy endpoints.

An intercurrent event is defined as receipt of systemic antibiotic rescue medication or discontinuation of study treatment due to an AE or lack of efficacy (See Section 8.2.2).

Receipt of systemic antibiotic rescue medication is defined as initiating any systemic antibiotic on or after Baseline for any reason (including in response to an AE). The only exception to this rule is if a participant randomized to the antibiotic stratum on a tetracycline antibiotic interrupts

their stable dose of tetracycline antibiotic during the study and subsequently restarts the same tetracycline antibiotic as confirmed using the coded preferred term. The restarted dose and frequency of the antibiotic must be the same or lower than the regimen prior to the interruption.

The dates of an intercurrent event are as follows:

- For receipt of systemic antibiotic rescue medication: start date of the antibiotic
- For discontinuation of study treatment due to an AE or lack of efficacy: Last study treatment date + 17 days. Note: study treatment discontinuation includes study discontinuation.

The choice of 17 days is intended to capture the interval between dosing and lesion assessments (14 days), as well as the visit window (3 days).

An additional sensitivity analysis will be conducted where missing data due to COVID-19 will be considered an intercurrent event and will be imputed as a nonresponse at that particular visit. This will be identified when there are missing data at a visit that has been impacted by COVID-19 according to the COVID-19 impact CRF page. The date of this intercurrent event will be the date of the impacted visit.

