6.4.2 Classification of participants as analgesic, antihistamine users

If a participant has taken a new analgesic/increased regimen of analgesic, or taken an antihistamine, on 1 or more days (need not be consecutive) in a study period (Initial Treatment Period or Maintenance Treatment Period), then for that period the participant will be classified as an analgesic or antihistamine user, respectively. The period under consideration is to match the period as defined for the HSSDD for the Initial Treatment Period or HSSQ for the Maintenance Treatment Period, based on dates/times of the medications taken.

New analgesic/increased regimen of analgesic use, regardless of indication, is defined as an analgesic medication with start date on or after the first dose of study medication. Stable

analgesics (ie, analgesics which were taken already before randomization) will not be included in this category of analgesic user. This classification will be used for selected subgroup analyses.

Antihistamine use is identified by considering the ATC classification. This classification is used for analyzing the Worst Itch endpoint and for selected subgroup analyses, by visit, for the Initial Treatment Period and Maintenance Period as applicable.

Additionally, if a participant has taken a new analgesic/increased regimen of analgesic on 1 or more days (need not be consecutive) prior to the Week 16 visit, then for that week the participant will be classified as an analgesic user. This classification will be used to adjust the formal analysis of the Worst Skin Pain secondary endpoints. If there is a visit date but no HSSDD available at the visit, then the analgesic/antihistamine user status for that week will be derived based on the visit date. If there is no visit available, then the weekly analgesic/antihistamine user status will default to the analgesic/antihistamine status for the overall study period.

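### An incomplete start date can turn a background systemic antibiotic into a Day 1 intercurrent event; for analgesics the same dates expose an unresolved conflict

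*SAP*

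**What the plan says.** Section 4.2.4 gives one set of rules for incomplete dates. For partially reported "start and stop dates for AEs and for medication use, the algorithms listed below will be followed". Three branches for start dates matter here.

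- Start wholly unknown: the date of first dose is used under the condition "If the stop date is unknown or not prior to the date of first dose of study medication".
- Only the year known: the date of first dose is used under the condition "If the year of first dose of study medication is the same as the year of the partial start date". Failing that, and failing a match with the year of a treatment switch, the rule is "Otherwise, use the 1st of January of the year of the partial start date".
- Month and year known: the date of first dose is used if both match it. Otherwise the switch date is used if that matches, and failing that the first of the month.

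Section 3.9 defines receipt of rescue antibiotic as "initiating any systemic antibiotic on or after Baseline for any reason". It dates the event thus: "For receipt of systemic antibiotic rescue medication: start date of the antibiotic". One exemption follows: "The only exception to this rule is if a participant randomized to the antibiotic stratum on a tetracycline antibiotic" interrupts a stable dose and restarts the same drug at the same or a lower regimen.

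Section 6.4.2 defines new or increased analgesic use by a start date on or after first dose, and then says: "Stable analgesics (ie, analgesics which were taken already before randomization) will not be included". The resulting status is a covariate in the models of Sections 8.3.4.1 and 8.3.5.1.

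**The concern.** The rules in Section 4.2.4 are a reasonable default for safety reporting, where an ambiguous record should be counted as on treatment. The same default is unsuitable for an event that defines the primary endpoint. Once a background antibiotic has an imputed start on the day of first dose, Section 3.9 reads it as initiated at Baseline, and an uninterrupted drug does not meet the tetracycline exemption.

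The consequences follow from other sections:

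- Section 4.2.1.1 sets HiSCR50 to nonresponse from that point on, even where lesion counts were observed.
- Section 4.2.1.2 carries this to HiSCR75 and pain response, and Table 8-2 counts the participant as having flared.
- Section 4.2.3.2 sets recorded DLQI and worst skin pain values to missing and imputes them.

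An observed responder would thus be overwritten because of an incomplete date field. Section 4.2.3.1 justifies the composite strategy by events that bear on outcome after study medication is received, and this is not such an event.

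**Working it through.** **Step 1. Apply the date rules.** Take an illustrative first dose on 15 June 2021 and a background antibiotic that is in truth older than that.

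| Recorded start | Imputed start | Antibiotic event under 3.9? |
|---|---|---|
| Unknown, ongoing | 15 Jun 2021 | Yes |
| Unknown, stopped after first dose | 15 Jun 2021 | Yes |
| 2021 only | 15 Jun 2021 | Yes |
| Jun 2021 | 15 Jun 2021 | Yes |
| Mar 2021 | 1 Mar 2021 | No |
| 2018 only | 1 Jan 2018 | No |

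The problem is confined to wholly unknown starts and to partial dates that match the year or month of first dose.

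**Step 2. Look for text that blocks the chain.** Section 6.4 classes a drug started before and continued after first dose as both prior and concomitant, so background antibiotics fall within 4.2.4. The same section refers partial dates to 4.2.4 and plans the summary of antibiotics that qualify as intercurrent events. No other date rule is given for those events. The SAP guards against imputed dates elsewhere: Appendix A (Section 12.1) bars them from the anaphylaxis algorithm, and Section 6.2 overrides an imputed diagnosis date that conflicts with confirmed eligibility. Section 3.9 has no such guard.

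**Step 3. Reproduce the SAP's power.** Table 2-1 gives 0.90 for HiSCR50 with rates 0.50 (N=140) and 0.25 (N=70), two-sided alpha 0.025. Using the pooled variance under the null:

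- Pooled rate = (140 × 0.50 + 70 × 0.25)/210 = 0.4167.
- SE under the null = √[0.4167 × 0.5833 × (1/140 + 1/70)] = 0.0722.
- SE under the alternative = √[0.25/140 + 0.1875/70] = 0.0668.
- Power = Φ[(0.25 − 2.241 × 0.0722)/0.0668] = 0.907.

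This agrees with 0.90. Unpooled variance gives 0.933 and a continuity correction 0.877.

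**Step 4. Add false events.** Assume a share f of every arm is forced to nonresponse, so each rate p becomes p(1 − f). The SAP gives no value for f; the range is assumed.

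| f | Participants of 490 | Rates (140 arm, placebo) | Power | Odds ratio |
|---|---|---|---|---|
| 0 | 0 | 0.500, 0.250 | 0.907 | 3.00 |
| 1% | 4.9 | 0.495, 0.2475 | 0.901 | 2.98 |
| 2% | 9.8 | 0.490, 0.245 | 0.896 | 2.96 |
| 5% | 24.5 | 0.475, 0.2375 | 0.878 | 2.91 |
| 10% | 49 | 0.450, 0.225 | 0.845 | 2.82 |

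For the pooled arm (280 against 70, rates 0.60 and 0.25), power stays at or above 0.997 throughout.

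**Step 5. Size of one false event.** The largest possible shift is 1/70 = 1.4 percentage points on placebo and 1/140 = 0.7 in the single arm, reached only if that participant would otherwise have responded. At the Table 2-1 rates the expected shift is 0.25/70 = 0.36 points on placebo, 0.50/140 = 0.36 in the single arm and 0.60/280 = 0.21 in the pooled arm.

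**Step 6. Analgesics.** For a drug with an affected start date, the date-based sentence of Section 6.4.2 makes it new. The sentence on stable analgesics excludes it if use before randomization is known. The section does not say which prevails.

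**The case against.** The best defence is one of scope. Section 4.2.4 opens by stating its purpose: to decide whether adverse events and medications fall on treatment, and in which period. Sections 3.9 and 6.4.2 do not refer to it. Section 3.9 speaks of initiating a rescue drug, and its exemption presupposes a known stable dose. A sensible programmer might never treat the stratum-defining antibiotic as newly started. This has weight, but no sentence says so, and Section 4.2.4 is the only date rule available.

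The effect is also visible. Listings show dates as reported, antibiotics that qualify as intercurrent events are summarised (Section 6.4), HiSCR is shown without handling of intercurrent events (Section 8.4.1.1), and the treatment-policy analysis (Section 8.2.3.4) avoids the problem. That stands in part. The NRI, reference-based, FAS, PPS, CFS, COVID-19 and CMH analyses all keep the composite rule, and the observed-case analysis drops the participant. The tipping-point analysis is asymmetric: a false event stays nonresponse on bimekizumab, but on placebo it becomes missing and is shifted towards response.

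A reader might infer that any long-standing drug is redated to Day 1. The rules do not support that, since a known earlier year or month is imputed before Baseline. A reader might also infer that the analgesic covariate must be wrong. The text supports only an unresolved conflict, because the stable-analgesic sentence gives the right answer where earlier use is known.

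**Conclusion.** The antibiotic chain holds on the text, for wholly unknown starts (with stop unknown or not before first dose) and for partial starts that match the year or month of first dose. The analgesic part is a conflict within Section 6.4.2 without stated precedence; it affects the two Worst Skin Pain models and not HiSCR50.

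The size is probably small, and the SAP does not give the number affected. If the share is equal across arms and unrelated to response, the effect shrinks slightly towards no difference: power 0.907 becomes about 0.90 at 1-2% affected and 0.88 at 5%. With 70 placebo participants a chance imbalance could run either way, and a false nonresponse on placebo favours the drug. A reader might take 1.4 or 0.7 points as the typical effect of one false event; these are maxima, and the expected shifts are about a quarter and a half of them. Nor do the documents support a claim of an inflated false-positive rate. The case for acting is that a written rule would overwrite observed primary-endpoint data for a clerical reason.

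**What to change.** Add one sentence to each of Sections 3.9 and 6.4.2: a start date imputed under Section 4.2.4 does not by itself create an antibiotic intercurrent event or new-analgesic status. Add that where other collected data show use before first dose, for example the Baseline antibiotic stratum, the start is treated as before first dose. Remaining cases are settled by blinded review before unblinding, with the decisions recorded. This also settles which sentence of Section 6.4.2 prevails.

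The cost is a few sentences, a small programming change and a short blinded review of the records concerned. No treatment rule, endpoint definition or sample size changes, and the safety use of Section 4.2.4 can stay as it is.
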